7.1 Demographic and Baseline Characteristics

For the subjects in ITT and safety analysis set, demographic information and Baseline values will be summarized by descriptive statistics. Categorical data will be summarized by number and percent; and quantitative data will be presented by n, mean, standard deviation, minimum value, median, and maximum value.

In general, continuous variables will be analyzed using analysis of variance (using SAS procedure 'PROC GLM') with treatment group as factor. Categorical variable will be analyzed using chi-square test or Fisher's exact test if $\geq 20\%$ of the cells have expected cell count < 5 .

The following demographic and Baseline values will be summarized.

Continuous Variables:

- Age (years)
- Body weight (kg)
- Height (cm)
- Body Mass Index (kg/m²)
- Blood Pressure (systolic/diastolic) (mmHg)
- Pulse (bpm)
- Temperature (°C)
- CDAI
- Average Daily Stool Frequency

- Average Daily Abdominal Pain
- Total SES-CD score
- Crohn's Disease Duration (years)
- hs-CRP mg/L
- Fecal calprotectin
- IBDQ score
- WPAI and its components
- EQ-5D
- Abdominal Pain Rating Scale
- Bristol Stool Chart Score
- Mean dose of corticosteroids for those on baseline corticosteroid use.

Categorical Variables:

- Sex (male, female)
- Race
- Ethnicity
- Age (< 40, 40 to < 65, 65 to < 75, \geq 75)
- Baseline corticosteroid use (yes, no)
- Baseline immunosuppressant use (yes, no)
- Number of prior immunosuppressant use
- Number of prior biologic use
- hs-CRP at Baseline (< 10 and \geq 10 mg/L)
- Baseline fecal calprotectin (\leq 250 μ g/g, $>$ 250 μ g/g)
- Crohn's disease severity (CDAI \leq 300, $>$ 300) at Baseline
- Baseline SES-CD (< 15, \geq 15)
- Disease duration (\leq 3 years, $>$ 3 years)
- Tobacco use (user, ex-user, never used, unknown)
- Alcohol use (drinker, ex-drinker, non-drinker, unknown)
- Region (US, ex-US)

7.2 Medical History

Medical and Surgical History: A complete medical and surgical history (which includes CD-onset date), history of tobacco and alcohol use, and TB history will be obtained from each subject during the Screening period. Medical history will be summarized using body system and condition/diagnosis by treatment group. No statistical tests will be performed.

Chest X-Ray Results: All subjects undergo a standard X-ray of chest (including a posteroanterior [PA] and lateral view) at Screening period. Number and percent of subjects with presence or absence of finding for the previous TB infection, calcified granulomas, Pleural scarring/thickening, and other findings will be presented by treatment group. No statistical tests will be performed.

TB Test Results: Results of PPD skin test, QuantiFERON-TB Gold test at screening visit will be summarized. Induration will be summarized descriptively using n, mean, standard deviation, minimum values, median, and maximum values. The frequency distribution of induration ≥ 5 and < 5 will be provided. QuantiFERON-TB tests will be described as positive or negative. Indeterminate QuantiFERON-TB test results will be repeated. If the second QuantiFERON-TB test is positive or indeterminate, the final assessment will be considered positive. If the second QuantiFERON-TB test is negative, the final assessment will be considered negative. No statistical tests will be performed.

TB Prophylaxis: History of use of TB Prophylaxis or initiation of TB prophylaxis will be summarized.

ECG Results: ECG results at screening will be presented as frequency distribution showing results as Normal, Abnormal (Not clinically significant), Abnormal (Clinically significant) and Unable to evaluate/missing. No statistical tests will be performed.

7.3**Previous Treatment and Concomitant Medications**

Based on generic medication names, these categories of medications used by subjects before and during the study will be summarized by number and percent for ITT and safety analysis sets for the treatment groups. No statistical tests will be performed.

The number and percent of subjects using Crohn's disease specific medications (including corticosteroids, aminosalicylates, immunosuppressants [defined as azathioprine, 6-mercaptopurine, or methotrexate], antibiotics) within past 90 days prior to the Baseline, and at the Baseline will be tabulated. In addition, the number and percent of subjects using Crohn's disease specific immunosuppressants, and biologic therapies at any time prior to Baseline will be tabulated.

8.0**Patient Disposition**

Subject disposition will be presented for subjects in the ITT and safety analysis sets using the following information by treatment group:

- Number and percent of subjects in various analysis sets by treatment group and by investigator and/or site number
- Number and percent of subjects completing extension phase and discontinuing on or before Week 52 visit.
- Subject disposition including the number and percent of subjects who prematurely discontinued the study) by primary reason and by any reason

Summary of protocol deviations will be provided.

9.0**Study Drug Exposure and Compliance**

Study drug exposure and compliance will be summarized using the mean, standard deviation, minimum, median, and maximum. Exposure to study drug will be summarized by separately for double-blind extension phase and open-label extension phase.

Compliance is defined as the number of capsules taken (i.e., the difference between the number of capsules dispensed and the number of capsules returned) divided by the number of capsules a subject is supposed to take each day times the length of time that the subject was in the Treatment Phase of the study (i.e., Final/Discontinuation Visit date during Treatment Phase – Day 1 [Baseline] Visit date + 1). Subjects with missing data for the number of capsules returned will be excluded from the summary.

10.0 Efficacy Analysis

10.1 General Considerations

All statistical tests will be two-sided with the significance level of 0.100. Descriptive statistics will be provided. These include the number of observations, mean, standard deviation, minimum, median, and maximum for continuous variables; and number and percent for discrete variables. The analysis will be performed using SAS® (SAS Institute Inc., Cary, NC, USA).

10.2 Efficacy Analyses

The endpoints (Double-Blind Extension Phase) include:

- Proportion of subject who achieve remission at Week 52.
- Proportion of subjects who achieve endoscopic remission at Week 52.
- Proportion of subjects who achieve both endoscopic remission and modified clinical remission at Week 52.
- Proportion of subjects who achieve clinical remission over time.
- Proportion of subjects who maintain clinical remission over time among subjects in clinical remission at Week 16.
- Proportion of subjects who achieve modified clinical remission over time.
- Proportion of subjects who maintain modified clinical remission over time among subjects in modified clinical remission at Week 16.
- Proportion of subject who achieve response at Week 52.
- Proportion of subjects with SES-CD ≤ 2 at Week 52.

- Proportion of subjects with SES-CD = 0 at Week 52.
- Proportion of subjects who achieve endoscopic response at Week 52.
- Proportion of subjects who achieve enhanced endoscopic response at Week 52.
- Proportion of subjects who achieve endoscopic improvement at Week 52.
- Proportion of subjects who achieve endoscopic healing at Week 52.
- Proportion of subjects who achieve clinical response over time.
- Proportion of subjects who achieve enhanced clinical response over time.
- Proportion of subjects who maintain enhanced clinical response over time among subjects in enhanced clinical response at Week 16.
- Proportion of subjects with an average daily SF ≥ 2.5 AND average daily AP ≥ 2.0 at Induction Baseline who achieve clinical remission over time.
- Proportion of subjects taking corticosteroids at Induction Baseline who discontinued corticosteroid use and achieved CDAI < 150 over time.
- Proportion of subjects taking corticosteroids at Induction Baseline who discontinued corticosteroid use and achieve remission at Week 52.
- Proportion of subjects taking corticosteroids at Induction Baseline who discontinued corticosteroid use and achieve clinical remission over time.
- Proportion of subjects taking corticosteroids at Induction Baseline who discontinued corticosteroid use and achieve modified clinical remission over time.
- Proportion of subjects taking corticosteroids at Induction Baseline who discontinued corticosteroid use and achieve endoscopic remission at Week 52.
- Proportion of subjects who achieve CDAI < 150 at over time.
- Proportion of subjects with decrease in CDAI ≥ 70 points from Induction Baseline over time.
- Change from Induction Baseline in fecal calprotectin level over time.
- Change from Induction Baseline in hs-CRP at over time.
- Change from Induction Baseline in IBDQ at Week 52.
- Change from Induction Baseline in EQ-5D at Week 52.
- Change from Induction baseline in EIMs at Week 52.

- Proportion of subjects with isolated ileal Crohn's disease who achieve remission at Week 52.
- Proportion of subjects with isolated ileal Crohn's disease who achieve modified clinical remission at Week 52.

For categorical efficacy endpoints for double-blind extension phase, the pairwise comparisons for the difference in proportions of subjects between ABT-494 3 mg BID group and ABT-494 higher dose groups will be analyzed using the Chi-square test (or Fisher's exact test if $\geq 20\%$ of the cells have expected cell count < 5 .). Additionally, the 95% confidence interval based on normal approximation for the difference in proportions will be provided.

The non-responder imputation will be used for subjects with missing data at the endpoint evaluated. The last observation carried forward (LOCF) method will also be used as the sensitivity analyses.

In general, continuous efficacy variables with repeated measurements will be analyzed using a Mixed Effect Repeated Measure (MMRM) model. The mixed model includes the categorical fixed effects of treatment, week and treatment-by-week interaction and the continuous fixed covariates of Induction baseline measurement. An unstructured variance-covariance matrix will be used. If convergence is not achieved, other variance-covariance matrix will be explored until coverage. The parameter estimations will be based on assumption of data being missing at random and using the method of restrictive maximum likelihood (REML).

Continuous secondary efficacy variables will also be analyzed using an Analysis of Covariance (ANCOVA) model including factors for treatment group, and Induction Baseline values as a covariate. The MMRM analysis is considered primary for inferential purposes.

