**8.1.6.2 Secondary Efficacy Variables****8.1.6.2.1 Analysis of Secondary Endpoints**

Secondary efficacy variables are divided into two groups. The first group includes double-blind induction treatment period secondary endpoints. Analyses for the first group of secondary endpoints will be performed using MITT analysis set. The second group includes double-blind extension phase secondary endpoints. Analyses for the second group of secondary endpoints will be performed using ITT-N and ITT-NR analysis sets.

For categorical secondary endpoints, the pairwise comparisons for the difference in proportions of subjects between treatment groups will be analyzed using the CMH test adjusted for randomization stratification variable(s), Crohn's disease severity (SES-CD  $< 15$ ,  $\geq 15$ ) at Baseline and prior anti-TNF use (naïve, experienced). Additionally, the CMH-based 95% confidence interval for the difference in proportions will be provided. The non-responder imputation will be used for subjects with missing data at the endpoint evaluated. The last observation carried forward (LOCF) method will also be used as the sensitivity analyses for the secondary endpoints.

In general, continuous secondary efficacy variables with repeated measurements will be analyzed using a Mixed Effect Repeated Measure (MMRM) model. Continuous secondary efficacy variables will also be analyzed using an Analysis of Covariance (ANCOVA) model including factors for treatment group and stratification variable, Crohn's disease severity (SES-CD  $< 15$ ,  $\geq 15$ ) at Baseline and prior anti-TNF use (naïve, experienced). Baseline values will be used as a covariate in the MMRM and ANCOVA models. The MMRM analysis is considered primary for inferential purposes.

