For all variables (categorical variables and continuous variables), the following rules will be used for the LOCF approach:

1. Extension Baseline and Pre-Baseline values will not be used to impute the missing Post-Baseline values.
2. Missing values after Study Day 1 will be imputed using the latest non-missing values after Day 1 and prior to the missing value. If there are no non-missing values after Baseline, then the LOCF value will be missing.

Observed Case (OC)

Observed case analysis will be performed such that missing values will not be imputed. However, all observed values will be replaced by Induction Baseline value once subjects received CD-related corticosteroid therapy, or value prior to open label therapy once subjects moved to open-label therapy.

Mixed-Effect Model Repeated Measure (MMRM)

The MMRM model will be used for continuous efficacy variables with longitudinal data as the primary analysis. The MMRM model includes the baseline values as covariate, treatment, time point and treatment-by-time point interaction as fixed effects; and subjects within treatment as random effect. An unstructured (co)variance structure will be used to model the within-subject error. The comparison at a time point will be the contrast between treatments at that time point. Satterthwaite's approximation will be used to estimate denominator degrees of freedom.

Imputation of Missing Dates

For Baseline, efficacy, and safety parameters, if the day and/or month are missing, the following conventions will be used to impute the missing dates:

- 01 for missing start day

- End of month for missing end day
- January 1st for missing start month
- December 31st for missing end month

In case of partially missing AE start and stop dates, the dates will be imputed by comparing to first dose date of study medication so that the corresponding AEs will be made treatment-emergent whenever possible. If the start date of an AE is partially missing and the month is the same as the start date of a new therapy, the AE will be made treatment emergent to the new therapy.

In case of missing or partially missing study drug dosing dates, the dates will not be imputed. Subjects will be treated as not receiving dose on that date.

Rule for CDAI Calculation

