The MMRM model will be used for continuous efficacy variables with longitudinal data as the primary analysis. The MMRM model includes the baseline values as covariate; randomization strata, treatment, time point and treatment-by-time point interaction as fixed effects; and subjects within treatment as random effect. An unstructured (co)variance structure will be used to model the within-subject error. The comparison at a time point will be the contrast between treatments at that time point. Satterthwaite's approximation will be used to estimate denominator degrees of freedom.

Imputation of Missing Dates

For Baseline, efficacy, and safety parameters, if the day and/or month are missing, the following conventions will be used to impute the missing dates:

- 01 for missing start day
- End of month for missing end day
- January 1st for missing start month
- December 31st for missing end month

In case of partially missing AE start and stop dates, the dates will be imputed by comparing to first dose date of study medication so that the corresponding AEs will be

made treatment-emergent whenever possible. If the start date of an AE is partially missing and the month is the same as the start date of a new therapy, the AE will be made treatment emergent to the new therapy.

In case of missing or partially missing study drug dosing dates, the dates will not be imputed. Subjects will be treated as not receiving dose on that date.

Rule for CDAI Calculation

Up to 14 days of diary entries will be evaluated from the ePRO tool for the CDAI calculation for each visit. The diary entries on the days the subjects receive endoscopy preparation medications, the day of endoscopy procedure, and 2 days after endoscopy procedure will be excluded. For each CDAI subscore, the available scores from the most recent diary days (at least 4 days, up to 7 days) prior to actual day of the study visit will be summed, and then multiplied by the corresponding multiplier to get subtotal score. If available diary entries are fewer than 7 days, the subtotal score will be calculated as (summed total available score/number of days) \times 7 \times corresponding multiplier. The three subtotal scores that are based on ePRO (number of liquid/very soft stools, abdominal pain rating, and general well-being) will then be rounded to one decimal. The final CDAI is rounded to a whole number.

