- The proportion of subjects who achieve $> 50\%$ reduction from Baseline in SES-CD or endoscopic remission at Week 12/16.
- The proportion of subjects who achieve modified clinical remission at Week 16 among subjects with an average daily SF ≥ 4.0 or average daily AP ≥ 2.0 at Baseline.

For categorical efficacy endpoints for Induction Period, the pairwise comparisons for the difference in proportions of subjects between treatment groups and placebo group will be analyzed using the CMH test adjusted for Crohn's disease severity (SES-CD < 15 , ≥ 15) at Baseline. Additionally, the CMH-based 95% confidence interval for the difference in proportions will be provided. The 95% confidence interval for the difference in proportions within each Crohn's disease severity (SES-CD < 15 , ≥ 15) at Baseline category will be calculated based on normal approximation.

The non-responder imputation will be used for subjects with missing data at the endpoint evaluated. The last observation carried forward (LOCF) method will also be used as the sensitivity analyses for the secondary endpoints.

In general, continuous secondary efficacy variables with repeated measurements will be analyzed using a Mixed Effect Repeated Measure (MMRM) model. The mixed model includes the categorical fixed effects of treatment, Crohn's disease severity (SES-CD < 15, ≥ 15) at Baseline, week and treatment-by-week interaction and the continuous fixed covariates of baseline measurement. An unstructured variance-covariance matrix will be used. If convergence is not achieved, other variance-covariance matrix will be explored until coverage. The parameter estimations will be based on assumption of data being missing at random and using the method of restrictive maximum likelihood (REML).

Continuous secondary efficacy variables will also be analyzed using an Analysis of Covariance (ANCOVA) model including factors for treatment group and Crohn's disease severity (SES-CD < 15, ≥ 15) at Baseline, and Baseline values as a covariate. The MMRM analysis is considered primary for inferential purposes.

The additional endpoints include:

- Proportion of subjects who achieve clinical remission over time in Induction Period.
- Proportion of subjects who achieve clinical response over time in Induction Period.
- Proportion of subjects who achieve CDAI < 150 over time in Induction Period.
- Proportion of subjects with decrease in CDAI ≥ 70 points from Induction Baseline over time in Induction Period.

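### The Extension SAP replaces the protocol's SES-CD-adjusted CMH analysis with an unadjusted test and a normal-approximation interval, without explaining or recording the change

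*SAP*

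**What the plan says.** Protocol Section 8.1.6.2.1 divides the secondary endpoints into an induction group and an extension group and gives one method for both.

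- Categorical endpoints: pairwise differences "will be analyzed using the CMH test adjusted for randomization stratification variable(s"), the variables being baseline SES-CD (<15, ≥15) and prior anti-TNF use. The 95% interval is CMH-based.
- Continuous endpoints: an MMRM, plus an analysis of covariance ("ANCOVA) model including factors for treatment group and stratification variable", the same two variables). For the MMRM the protocol names only the baseline value as a covariate.

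Extension SAP Section 10.2 differs.

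- Categorical endpoints: the differences "between ABT-494 3 mg BID group and ABT-494 higher dose groups will be analyzed using the Chi-square test", or by Fisher's exact test if at least 20% of cells have an expected count below 5. In addition, "the 95% confidence interval based on normal approximation for the difference in proportions will be provided", with no alternative for sparse tables.
- Continuous endpoints: "ANCOVA) model including factors for treatment group, and Induction Baseline values as a covariate". SES-CD is gone.
- Section 10.1 sets all tests at a two-sided 0.100 level.

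Extension SAP Section 4.2 explains why prior anti-TNF use was dropped: fewer than 10 naïve subjects were enrolled under Amendment 3. It does not mention SES-CD. The Induction SAP drops anti-TNF for the same reason, yet its Section 10.3 retains the "CMH test adjusted for Crohn's disease severity". Extension SAP Section 12.1, which lists differences from the protocol, contains only added efficacy variables.

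**The concern.** A pre-specified adjustment and its matching interval have been replaced, and a reader of Section 12.1 would not know it. Two things are at stake.

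First, if SES-CD severity predicts outcome and is unbalanced by chance between the re-randomized doses, the unadjusted comparison attributes part of that imbalance to dose.

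Second, the SAP recognises sparse tables when it chooses the test but not when it chooses the interval. Sparse tables are plausible for endpoints such as SES-CD = 0, or remission in isolated ileal disease, analysed separately in Week 16 responders and non-responders with induction-placebo subjects set apart. There, a 95% interval can exclude zero beside a test that fails even at 10%, or can have zero width.

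**Working it through.** **No plan figure to reproduce.** The only stated power (at least 80%, 35 per group) is for the induction dose-response test. The documents give no size, rate or power for the extension comparisons. All arm sizes and rates below are therefore assumptions.

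**Departures from the protocol**

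- Categorical test: CMH adjusted for SES-CD becomes unadjusted chi-square/Fisher. A departure, not explained.
- Interval: CMH-based becomes normal approximation. A departure, not explained.
- ANCOVA: SES-CD removed. A departure, not explained.
- Prior anti-TNF: removed. A departure, explained in Section 4.2.
- MMRM: the Induction SAP has "randomization strata, treatment, time point and treatment-by-time point interaction as fixed effects"; the Extension SAP "includes the baseline values as covariate, treatment, time point and treatment-by-time point interaction as fixed effects". The two SAPs differ, but the protocol never put strata in the MMRM, so this is not a departure from it.

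**Value of the SES-CD adjustment.** Assume a 30% overall rate and half of the subjects at SES-CD ≥15.

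- Share of the unadjusted variance that lies between severity strata = (gap/2)² / (0.3 × 0.7). For gaps of 10, 20 and 30 points: 0.0025/0.21 = 1.2%, 0.01/0.21 = 4.8%, 0.0225/0.21 = 10.7%.
- SD of the chance imbalance at 22 per arm = √(2 × 0.25/22) = 0.151. A 2-SD imbalance of about 30 percentage points shifts the unadjusted difference by 0.30 × gap = 3, 6 or 9 points.
- Simulated power (40,000 trials, two-sided 0.10, control rates 45%/15% by stratum, +25 points in both). Unadjusted: 37.8, 51.4 and 79.5% at 15, 22 and 45 per arm. CMH with exact fallback: 41.0, 54.7 and 81.5%. Gain: 3.2, 3.3 and 2.0 points.
- With control rates 40%/20%, unadjusted 37.9, 51.4, 79.9% and CMH 39.4, 52.7, 79.7%. Gain: 1.5, 1.3 and −0.2 points.
- A separate set of assumptions (odds ratio 3, 20 to 45 per arm) gives −1.0 to +7.6 points. The top value needs a 40-point severity gap at 20 per arm.

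**Behaviour of the interval.** Exact binomial enumeration with equal arms and the SAP's own test rule. In a 2×2 table one cell is 25% of the cells, so a single expected count below 5 triggers Fisher.

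| Assumed 2% vs 10% | n = 15 | n = 20 | n = 30 |
|---|---|---|---|
| Coverage, normal approximation | 78.5% | 87.1% | 92.6% |
| Coverage, Newcombe | 99.8% | 99.1% | 99.0% |
| Coverage, Miettinen–Nurminen | 99.0% | 98.5% | 98.0% |
| Normal interval excludes 0 but P > 0.10 | 0% | 6.0% | 11.3% |

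- 0/20 vs 4/20: difference 0.20, SE = √(0.2 × 0.8/20) = 0.0894, and 0.20 ± 1.96 × 0.0894 gives 2.5 to 37.5 points. Fisher P = 0.106. Newcombe gives −0.1 to 41.6.
- 0/10 vs 3/10: normal interval 1.6 to 58.4 points, Fisher P = 0.211. Newcombe gives −3.8 to 60.3.
- Both rates 2% at 15 per arm: the interval has zero width in 54.5% of trials.
- 20% vs 40% at 15 per arm: coverage is 93.1%, so serious under-coverage belongs to sparse tables.

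**Limits of the remedy**

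- 2/15 vs 7/15: Fisher P = 0.109, yet Newcombe still excludes zero (0.5 to 58.5 points). At 20% vs 40% with 15 per arm this conflict occurs in 4.1% of trials with either interval.
- A 95% interval beside a 10% test also disagrees the other way: 4/30 vs 10/30 has P = 0.067 with a normal interval of −0.8 to 40.8. At 20% vs 40% with 30 per arm, such disagreement occurs in 10.0% of trials with the normal interval and 13.1% with Newcombe.

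**The case against.** The strongest reply is that the adjustment hardly matters. SES-CD was not a stratum at the Week 16 re-randomization (Extension SAP Section 5.2), and overall response, which was, is handled by analysing responders and non-responders separately. At 45 per arm with a 20-point severity gap, CMH is no better. At 15 per arm, part of its gain reflects a type I error closer to nominal (7.8% vs 6.0%, against 10%). These are Phase 2 extension endpoints without multiplicity control. All of this stands, and it limits the size of the point. But the SAP does not make the argument, and it does not answer the interval problem.

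A reader might go further in four ways that the documents do not support.

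- *The unadjusted test is invalid.* It is not; the loss is some precision and protection against chance imbalance. Induction dose, which was a Week 16 stratum, is not adjusted for in the protocol's test either.
- *The MMRM also breaks the protocol.* The protocol does not name strata for it.
- *Changing the interval removes every contradiction.* The 2/15 vs 7/15 table shows otherwise.
- *The 24 mg QD comparison is biased by non-concurrent controls*, because 6 mg BID replaced that dose at Amendment 2. The SAP does not say whether 24 mg QD is among the higher-dose groups, and the documents give neither the allocation of 3 mg BID over time nor any drift in outcome. The one documented change in population, with assumed figures (9 of 150 subjects, a 40-point gap), gives 9/150 × 40 = 2.4 points of drift. If 10 to 30% of 3 mg BID controls came from the earlier scheme, the bias is 0.7 to 0.9 × 2.4, or 1.7 to 2.2 points, with null rejection of 2.7 to 8.1% against a nominal 10%. Larger error rates require drifts of 10 to 30 points that nothing in the documents suggests.

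**Conclusion.** The point holds as an unrecorded departure from the protocol with a poor choice of interval. The departure (CMH to chi-square/Fisher, the CMH-based interval to a normal approximation, SES-CD out of the ANCOVA) is read directly from the documents and needs no assumption.

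Its effect through the lost adjustment is small: about 0 to 3 power points for severity gaps of 20 to 30 points, more only if severity is very strongly prognostic, and a shift of 3 to 9 points under a 2-SD imbalance at 22 per arm. The interval defect is larger but confined mainly to sparse tables: coverage as low as 78.5%, and contradictions with the SAP's own test in up to 11.3% of trials under the 2% vs 10% assumption. How often such tables will arise cannot be told, because extension arm sizes and rates are not given. The consequence is limited to how Phase 2 extension results are read; it does not touch the co-primary induction analysis.

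**What to change.** 1. In Extension SAP Section 10.2, use CMH adjusted for baseline SES-CD (<15, ≥15), with an exact stratified version where the Fisher rule now applies. Keep SES-CD in the ANCOVA, and in the MMRM for consistency with the Induction SAP. If the unadjusted analysis is preferred, give the reason. Either way, list every remaining departure from the protocol's methods, including the anti-TNF removal, in Section 12.1.
2. Replace the normal-approximation interval with Miettinen–Nurminen or Newcombe, in stratified form if CMH is used.
3. Add a 90% interval to match the two-sided 0.10 test, or state that the 95% interval is descriptive. Matching the level does not guarantee agreement beside Fisher: for 0/10 vs 3/10 the 90% Newcombe interval is 2.6 to 55.8 points with P = 0.211. Full agreement needs an interval obtained by inverting the reported test.
4. State whether 24 mg QD is among the higher-dose groups.

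The cost is SAP text and modest programming. No new data are needed, since the SES-CD category is already a listed baseline characteristic in Extension SAP Section 7.1. The drawback is that the proposed intervals are conservative in sparse tables (coverage 98 to 99.8% in the cases above).
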